### 4.1.2. Investigation schedule

Table (4.1.2) 1 describes the measurement of efficacy and safety assessed during the study

Table (4.1.2) 1 - Investigation schedule

	Screening visit	Screening period – Inclusion	Induction phase							Withdrawal/ End-of-study			
			D3	D4	D5	D8	D10	D12	D17	D21	D24	D28	visit
Informed consent	X												
Screening criteria	X												
Height / Weight / BSA		X	X										
Inclusion / exclusion criteria		X											
Relevant medical / surgical history	X												
Previous treatments	X												i
Concomitant treatments	X		X	X	X	X	X	X	X	X	X	X	X
Pregnancy test (serum)		X											X
IRS randomization		X											
S95014 administration			X (see section 6.1)										
NIMP administration			(411 411 411 )	See Appe	rdix 1						l		
Pharmacokinetic assessment		l		вее пррег	uix 1								
Blood samples	I	I	X pre-dose, just after the infusion, 4h after the	X	X	X	X	X	X	X		X	
blood samples			end of infusion		48h after the end of infusion	Λ	Λ	Λ	Λ	Λ		Λ	
Pharmacodynamic assessment													
Plasma Asparaginase Activity							$X^2$		$X^2$	$X^2$		$X^2$	
Immunogenicity assessment													
Blood samples			X pre-dose						X			X	 
Safety assessments													
Vital signs		X	X pre-dose, post-infusion										X
Physical examination / ECOG		X	X pre-dose, post-infusion							 	 		X
ECG		X		X (see secti	ion 8.2)								X
Cardiac imaging 		X											X
Adverse events		X		X									X
Laboratory examinations													
Blood haematology		X	X				X		X		X		X
Blood biochemistry		X	X				X		Х		X		X
Blood coagulation		X	X				X		X		X		X
Urinary biochemistry		X	X				X		X		X		X
Hepatitis serology		X											X

<sup>2 Samples collected for PAA assessment will be the same as for PK assessment to avoid duplicating sample collection

For further practical details, methods of measurement are provided in sections 7, 8 and 9.

The maximum total volume of blood collected per participant during the study will be 200 mL. Additional blood samples will be collected in the frame of the ALL-MB 2015 protocol, as per local practice.

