## Clinical examination and vital signs measurements

- Serum pregnancy test will only be performed for WOCBP (see Section 5.5)
- Complete clinical examination, height and weight measurement and ECOG PS assessment will be performed
- Vital signs measurements include blood pressure (BP), heart rate (HR) and temperature. BP and HR will be measured by an automatic device in supine position after 5 min rest.

Vital signs and performance status measurements will be performed during screening, before and after S95014 infusion (Day 3, pre-dose and post-dose) and during the withdrawal/end-of-study visit.

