#### Laboratory tests

All laboratory tests performed during the study period will be assayed in an identified laboratory at hospital. Inter-visits laboratory tests could be assayed by local laboratories. In all cases, the full validated set of normal ranges values will be collected, as well as any update in these values during the study and must be documented in the corresponding eCRF pages.

All samples will be destroyed after mandatory assessment is completed and at the latest before the final version of the clinical report.

The laboratory parameters collection plan is described in Table (8.2) 1.

Blood haematology, blood biochemistry, blood coagulation and urinary analysis will be performed during screening, before S95014 infusion (Day 3, pre-dose), at Day 10, Day 17, Day 24 and during the withdrawal/end-of-study visit.

Other laboratory tests (i.e. hepatitis serology and pregnancy test) will be performed during screening and during the withdrawal/end-of-study visit.

**Test Category** Test Name Haematology Haematocrit, Haemoglobin, Red blood cells (RBC), White blood cells (WBC), Platelets, Differential (Basophils, Eosinophils, Lymphocytes, Monocytes, Neutrophils, Blasts in absolute value and in %) Albumin, Alkaline Phosphatase (ALP), ALT, AST, Ammonia, Bicarbonates, Gamma-Biochemistry glutamyl-transferase (GGT), Lactate dehydrogenase (LDH), Calcium, Phosphorus, Sodium, Potassium, Creatinine, Total Bilirubin, Total Cholesterol, LDL, HDL, Triglycerides, BUN or Urea, Uric Acid Amylase, Lipase, Glucose Urinary analysis Macroscopic Panel (Dipstick) (Blood, Glucose, Ketones, Protein) If the dipstick test is at least 2+ on one or more parameter(s), quantitative urinary biochemistry tests will be performed on the abnormal parameter(s) Prothrombin time - International Normalized Ratio (INR), fibrinogen, protein S activity, Blood coagulation antithrombin activity, activated Partial Thromboplastin Time (aPTT), D-dimer, FDP HbsAg, HbsAb, HbcAb, if HbsAg or HbcAb positive check viral load (HBV-DNA) at Hepatitis serology baseline, HCV RNA-PCR, HEV RNA-PCR Pregnancy Test Pregnancy testing is mandatory at inclusion (serum) and at withdrawal/end-of-study visit (serum) for WOCBP

Table (8.2) 1 - Local Clinical laboratory parameters collection plan

All samplings for biochemistry should be taken in fasting conditions.

Abnormal laboratory values or test/exams results (i.e. ECG recording) will constitute an AE if they are:

- associated with signs and symptoms, or

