1.2.1. Study plan

Each patient will be randomly assigned (1:1) to either lyophilized (arm 1) or liquid (arm 2) S95014 intravenously at the dose of 2500 U/m² at Day 3, in combination with other backbone chemotherapy agents as per local practice.

The study duration will be approximately 1.5 month, including the screening (14 days) and the treatment period consisting of the induction phase (approximately 30 days). After completing the induction phase, patient will be discontinued from the study and, provided that the inclusion/non-inclusion criteria are fulfilled, will be proposed to enter into a roll-over study (CL2-95014-003) for the consolidation phase.

[figure not shown]
The study will be divided into the following periods for each participant:

- **Screening visit (up to 14 days prior to inclusion):** to obtain informed consent and check the screening/non-screening criteria.
- **Screening period (Day -14 to Day -1):** to check the eligibility of the patient to be included in the study within 14 days prior to the inclusion.
- **Inclusion visit (Day 0):** to check inclusion/non-inclusion criteria and to confirm inclusion of the patient in the study

- **Randomization (Day 0):** the day of inclusion visit (i.e. Day 0), included subjects will be randomly assigned to one of the two treatment groups:
 - Lyophilized S95014 (arm 1)
 - Liquid S95014 (arm 2)
- **Infusion (Day 3):** the day of S95014 infusion, based on randomized treatment group.
- **Treatment period:** treatment period will start from the day of S95014 infusion, corresponding to Day 3 of the induction phase, until the withdrawal/end-of-study visit.
- **Withdrawal/End-of-study visit:** at least 30 days after S95014 infusion (i.e. Day 33) and before starting the consolidation phase. During the withdrawal/end-of-study visit, subjects will be proposed to participate in a roll-over study (CL2-95014-003) for the consolidation phase using lyophilized S95014 in combination with backbone regimen as per ALL-MB 2015 protocol.

The study plan is shown in Figure (1.2.1) 1.

Figure (1.2.1) 1 - Study plan

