3.1.2. General definitions

Unless specified otherwise in section 3.3 to 3.5, the following definitions will be considered:

- Analysable value will be defined as any non-missing value.
- Baseline value will be defined as the last analysable value prior to the first IMP intake (i.e. before or the same date as the first IMP intake date).
- Post-baseline value will be defined as any value recorded at a given timepoint after baseline.
- Change from baseline will be defined as the arithmetic difference between a post-baseline value and the baseline value for a given variable at a given time point.

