3.5. Pharmacokinetics analysis

The pharmacokinetic analysis will be performed on the Pharmacokinetic Analysis Set (PKAS). The PKAS is defined as all included participants having completed the treatment period without deviation affecting pharmacokinetic interpretation.

Final analysis will be performed after the database lock and the electronic transfer of PK data (i.e. PAA). The dataset needed for final analysis will be prepared by extraction under the supervision of Clinical Data Management Department from the I.R.I.S database.

A non-compartmental pharmacokinetic analysis will be performed on the individual PAA-time profiles, using the actual administration and sampling times after IMP administration. Calculated PK parameters will be described according to a separate Data Analysis Plan (DAP) such as: area under the PAA-time curve from time 0 to the time of the last observed non-zero PAA ($AUC_{0-T_{last}}$); area under the PAA-time curve from time 0 extrapolated to infinity (AUC_{inf}); percent of AUC_{inf} extrapolated ($AUC\%_{ext}$); maximum observed PAA (C_{max}); time to maximum PAA (T_{max}); observed PAA 14 days post-dose($C_{day\ 14}$); last observed PAA (C_{last}); time to last observed PAA (T_{last}); terminal half-life ($T_{1/2}$). The above PK parameters will be calculated for each patient (details of the PK parameter derivation will be specified in a separate document) and the corresponding descriptive statistics of PK parameters will be tabulated by treatment group (e.g. number of subjects, arithmetic mean, SD, geometric mean, geometric CoV, median, min, max).

Descriptive statistics of PAA (e.g. number of subjects, arithmetic mean, geometric mean, % coefficient of variation [%CV], SD, minimum, median, and maximum) will be also calculated and tabulated per nominal sampling time by treatment group. Plasma asparaginase activity over time will be plotted in semilogarithmic and linear formats as mean \pm SD and as median (Q1, Q3), using the nominal timepoints.

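### Does the SAP's date-based gloss on baseline let post-infusion Day 3 values become the reference?

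*SAP*

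**What the plan says.** SAP 3.1.2 defines baseline as the "last analysable value prior to the first IMP intake (i.e. before or the same date as the first IMP intake date". Any non-missing value counts as analysable. The companion entry reads "Post-baseline value will be defined as any value recorded at a given timepoint after baseline", so it is anchored to baseline and not to the infusion. These definitions apply unless SAP 3.3 to 3.5 say otherwise. Those sections do not redefine baseline, and safety sits in 3.6.

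Protocol 8.2 has vital signs and performance status measured "during screening, before and after S95014 infusion (Day 3, pre-dose and post-dose) and during the withdrawal/end-of-study visit". In the investigation schedule (Protocol 4.1.2), the Day 3 entries for vital signs and for physical examination/ECOG both read "X pre-dose, post-infusion". Laboratory panels are taken at screening and then "before S95014 infusion (Day 3, pre-dose), at Day 10, Day 17, Day 24 and during the withdrawal/end-of-study visit".

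**The concern.** The abbreviation in the parenthesis signals a restatement, yet the restatement is wider than the rule it restates. A reading taken half an hour after the infusion is not prior to dosing, but it does carry the dosing date. Because the rule takes the last qualifying value, a programmer who codes only the date condition would pick the post-infusion reading whenever both exist. For vital signs and ECOG, both exist in every patient who follows the schedule. The post-baseline definition gives no independent cut, since it moves with whatever was chosen as baseline.

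Two programmers could therefore derive different baselines from the same text. In principle an early effect of the drug could be absorbed into the reference value, and a change from baseline or a laboratory shift would then look smaller than it was.

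**Working it through.** The plan states no figure that depends on this definition, so the check applies both halves of the rule to the schedule and then looks for outputs that use the result.

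**Step 1: which value each rule selects.** Take, as an assumed example, an infusion from 10:00 to 11:00. The time rule keeps the last value before 10:00. The date rule keeps the last value dated on or before Day 3. Post-baseline time points = scheduled time points minus those up to and including baseline.

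| Measure | Scheduled time points | Time rule | Date rule |
|---|---|---|---|
| Vital signs, ECOG | 4: screening, Day 3 pre-dose, Day 3 post-infusion, end of study | Day 3 pre-dose; 4 − 2 = 2 post-baseline | Day 3 post-infusion; 4 − 3 = 1 post-baseline |
| Laboratory panels | 6: screening, Day 3 pre-dose, Days 10, 17 and 24, end of study | Day 3 pre-dose; 6 − 2 = 4 | Day 3 pre-dose; 6 − 2 = 4 |
| Antibodies | 3: pre-dose, Day 17, Day 28 | pre-dose; 3 − 1 = 2 | pre-dose; 3 − 1 = 2 |
| Asparaginase activity, Day 3 samples | pre-dose, end of infusion, 4 hours | pre-dose | 4-hour sample |

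So the rules differ for vital signs, ECOG and the activity samples, and agree for scheduled laboratory and antibody data.

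**Step 2: which named outputs use the baseline where the rules differ.**

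- *Activity and PK.* SAP 3.5 derives AUC and Cmax from each profile "using the actual administration and sampling times after IMP administration", and tabulates activity by nominal time. The ANOVA contains only a formulation effect. No baseline enters.
- *Vital signs.* SAP 3.6.2 summarises them by time point. Pre-dose and post-infusion are separate time points, so each is reported as itself.
- *ECOG and physical examination.* SAP 3.6.2 names no output for them, and neither they nor vital signs are in the baseline characteristics of SAP 3.3.3.

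Named outputs that change on scheduled data: 0.

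**Step 3: unscheduled laboratory samples.** The laboratory shift tables in SAP 3.6.2 do use baseline. Protocol 8.2 says "Inter-visits laboratory tests could be assayed by local laboratories". That sentence concerns where samples taken between visits may be assayed. Day 3 is itself a scheduled day, so it does not clearly describe a second Day 3 sample after dosing. Suppose one exists. Under the date rule it becomes the reference. It does not leave the worst-value window, because SAP 3.6.2 takes the worst value over the treatment period, and SAP 1.2.1 says the "treatment period will start from the day of S95014 infusion". The table's row could change for that patient; the worst-grade column could not. Treatment-emergent events are counted from the infusion (SAP 3.6.1), so an adverse event arising after dosing is still captured.

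**The case for a change.** The strongest case for amending is that the parenthesis is the part written in terms that can be coded directly, so a programmer may reasonably treat it as the working rule. Nothing in SAP 3.6 adds a pre-dose condition. SAP 3.1.2 does define change from baseline, and the table templates are in a separate document that cannot be seen here; they might apply it to vital signs. Clearer wording would take one sentence, and the infusion time is already needed for the PK analysis.

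Part of this stands. The gloss is wider than the rule, and the text does not limit it to pre-dose values. But selecting a post-infusion value means discarding the main clause altogether. The parenthesis has an obvious purpose: the intended baseline samples are taken on the dosing date, and a strict earlier-date rule would throw them out. The Day 3 vital signs are scheduled as pre-dose and post-infusion assessments, so the data structure points to the right one. If the templates did include change from baseline for vital signs, the same rule would apply to both arms of a randomised comparison, in a descriptive table. For unscheduled laboratory samples, the documents do not show that a clock time or pre-dose label is recorded, so a stricter rule could also discard a genuine same-day pre-dose value.

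**Conclusion.** No change is needed. The definition is ambiguous on one day, and its natural reading, the last value before dosing with same-day pre-dose values allowed, is the one an analyst would use. The count of 2 versus 1 post-baseline time points for vital signs and ECOG is correct, but it feeds no analysis that the SAP names. Primary PK, treatment-emergent events, scheduled laboratory shifts and immunogenicity are the same under either reading.

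The residual exposure is the reference category in a laboratory shift table for any patient with an unscheduled post-infusion sample on Day 3. The documents give no number of such patients, and it may be 0. The conclusion assumes that the separate table templates add no change-from-baseline output for vital signs or ECOG. If they do, the effect stays within descriptive safety tables, and the programming specification can settle it by taking the value scheduled as pre-dose.

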3.2. Handling of Missing, Unused, and Spurious Data

No specific imputation method will be used for missing data, unless otherwise specified.

Adverse events (AEs)

- Handling of unknown causality assessment:
 - o If a subject experience an AE with a missing causality assessment, the relationship of the AE will be counted as "related".
- Handling of unknown severity grades:
 - o If a subject experiences more than one AE categorized under the same preferred term, one of them is categorized as "severe" and one of them is categorized as "unknown", the severity of this AE should be counted as "severe".
 - o If a subject experiences more than one AE categorized under the same preferred term, one of them is categorized as "mild" or "moderate" and one of them is categorized as "unknown", the severity of this AE should be counted as "unknown". A column "UNK" should be inserted for those AEs at the end of the table (before the "Total" column if applicable).

Immunogenicity

Missing baseline anti-drug antibody results will be imputed as negative.

Missing dates

If no specific management of dates is defined, missing information is substituted as shown below:

Table (3.1.2) 1 - Substitution rules of dates if no specific management is defined

| Date to substitute | Substituted date |
|--------------------|------------------|
| Date | ./mmm/yyyy |
| | ./.../yyyy |
| | ./.../.... |
| | No substitution |

Note:

./mmm/yyyy = missing day
 ./.../yyyy = missing day and month
 ./.../.... = missing date

3.3. Disposition and baseline characteristics

Disposition of subjects and baseline characteristics will be described by treatment group, to assess their comparability, and overall.

3.3.1. Disposition of subjects

Subject disposition will be tabulated for all subjects by summarizing the number and percentage of subjects who are included in each analysis set, randomized, completed study treatment, discontinued from the study and by the primary reason for discontinuation.

A listing will present dates of study discontinuation and the primary reason, if applicable for each subject.

3.3.2. Protocol deviations

Important protocol deviations will be summarized for the full analysis set by treatment group, using the number and percentage of subjects who had each type of deviation for the SAS. COVID-19 related protocol deviation will be also summarized. Protocol deviations will be reviewed by the sponsor prior to the database lock. In addition, these protocol deviations will be listed:

- Inclusion/Exclusion criteria not respected
- Study Withdrawal criteria not respected
- Study Treatment: incorrect dose or wrong treatment
- Primary Endpoint interpretation may be compromised
- Safety/Rights affected

3.3.3. Demographic data and other baseline characteristics

Demographic and baseline measurements will be summarized for the safety analysis set and the pharmacokinetic analysis set, using standard descriptive summaries or categorical summaries, as appropriate. In addition to the summary tables, a listing will be provided for all demographic and baseline characteristics data. In addition, listing of medical history will be provided.

The following baseline characteristics will be summarized based on descriptive statistics:

- Age at screening (years; if not available, then it will be calculated as the biggest integer $\leq [(ICF\ date - date\ of\ birth + 1) / 365.25]$)

- As continuous variable
- By categories (age <10, 10 - <16, and >= 16 years)
- Sex
- Race
- Ethnicity
- Height (cm)
- Weight (kg)
- Body Mass Index (BMI (kg/m²) = weight (kg) / height (m)²)
- Body Surface Area (BSA(m²) = sqrt (height (cm) x weight (kg) / 3600))

Baseline disease characteristics will be separately tabulated in a similar fashion for the following variables:

- ALL subtype and therapeutic group (B-Cell type Acute Leukemia (therapeutic groups: A/B/C/D1/D2/F/1221-SR/1221-IR)/E / T-Cell type Acute Leukemia (therapeutic groups: F/T-SRG/T-ImRG/T-HRG)

3.4. Treatments of subjects

3.4.1. Extent of exposure

Each patient will receive either lyophilized (arm 1) or liquid (arm 2) S95014, per the randomization at D000, intravenously over 1-hour at the dose of 2500 U/m² at Day 003 during the induction phase. Exposure to test drug for each subject will be listed. The following metrics will be summarized:

- Total exposure (U)
- Relative dose intensity (RDI): total exposure (U) / (2500 U/m² x BSA)

The safety analysis set will be used for exposure analysis. Listings of all dose change/interruption and reasons will be produced.

3.4.2. Concomitant treatments

Concomitant medication for each subject in the safety analysis set will be listed.

3.5. Pharmacokinetics analysis

The pharmacokinetic analysis will be performed on the Pharmacokinetic Analysis Set (PKAS). The PKAS is defined as all included participants having completed the treatment period without deviation affecting pharmacokinetic interpretation.

Final analysis will be performed after the database lock and the electronic transfer of PK data (i.e. PAA). The dataset needed for final analysis will be prepared by extraction under the supervision of Clinical Data Management Department from the I.R.I.S database.

A non-compartmental pharmacokinetic analysis will be performed on the individual PAA-time profiles, using the actual administration and sampling times after IMP administration. Calculated PK parameters will be described according to a separate Data Analysis Plan (DAP) such as: area under the PAA-time curve from time 0 to the time of the last observed non-zero PAA ($AUC_{0-T_{last}}$); area under the PAA-time curve from time 0 extrapolated to infinity (AUC_{inf}); percent of AUC_{inf} extrapolated ($AUC\%_{ext}$); maximum observed PAA (C_{max}); time to maximum PAA (T_{max}); observed PAA 14 days post-dose($C_{day\ 14}$); last observed PAA (C_{last}); time to last observed PAA (T_{last}); terminal half-life ($T_{1/2}$). The above PK parameters will be calculated for each patient (details of the PK parameter derivation will be specified in a separate document) and the corresponding descriptive statistics of PK parameters will be tabulated by treatment group (e.g. number of subjects, arithmetic mean, SD, geometric mean, geometric CoV, median, min, max).

Descriptive statistics of PAA (e.g. number of subjects, arithmetic mean, geometric mean, % coefficient of variation [%CV], SD, minimum, median, and maximum) will be also calculated and tabulated per nominal sampling time by treatment group. Plasma asparaginase activity over time will be plotted in semilogarithmic and linear formats as mean \pm SD and as median (Q1, Q3), using the nominal timepoints.

Bioequivalence tests will be used to compare the primary endpoints (AUC and C_{max}) in lyophilized formulation versus liquid formulation using the PKAS. Individual values of C_{max} , $AUC_{0-T_{last}}$ and AUC_{inf} will be logarithmically transformed prior to statistical analysis. An additional comparison will also be performed on $C_{day\ 14}$ for information purpose. To be specific, an analysis of variance (ANOVA) will be performed for the natural logarithms of PK parameters ($AUC_{0-T_{last}}$, AUC_{inf} , C_{max} and $C_{day\ 14}$). The ANOVA model will include fixed effect for formulation. The two one-sided tests procedure will be performed on the geometric mean ratio (GMR) between test (lyophilized pegaspargase) and reference (liquid pegaspargase) treatments. This will be done via a 90% confidence interval for the ratio obtained in the framework of the ANOVA for the logarithms. The confidence interval will be obtained by exponentiation of the upper and lower 90% confidence limits for the difference of logarithm means. PK comparability between the test treatment and the reference treatment will be concluded if the 90% confidence interval for AUC and C_{max} GMR is within the [80.00%; 125.00%] range.

Exploratory analysis may be performed to evaluate potential covariates impacting the PK parameters.

